3.4 Endpoints

All codes relevant to abstracting diagnostic, drug, and laboratory data appear in Appendix 1.

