3.4.1 Use of rosiglitazone in persons with contraindications

These outcomes will be ascertained using the Danish National Registry of Patients in Denmark and using the GPRD's Event File in the UK.

Using data on inpatient and outpatient hospitalizations, we will ascertain proportions of rosiglitazone users with the following conditions recorded before the first prescription for rosiglitazone (since 1977 in Denmark, since 1987 in the UK):

- History of heart failure or ischemic heart disease;
- History of acute coronary syndrome;
- History of peripheral vascular disease
- History of acute myocardial infarction;
- History of hepatic impairment (moderate to severe liver disease);

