3.6.2 Contraindications for use and off-label use

Prevalence of contraindicated or off-label use will be examined according to calendar time, where events marking relevant scientific publications and regulatory decisions will be marked. We will

report the number and proportion of patients prescribed rosiglitazone who had a diagnosis consistent with a contraindication for rosiglitazone use or with off-label use as defined in the Methods. We will provide the proportions in each country and over time. We will follow the analytic methods described above, provided that the sample size is large enough. At a minimum, use by patients with the additional contraindications (ischemic heart disease and/or peripheral vascular disease) listed in the 2008 press release¹⁰ will be examined in the periods before and after the publication of the press release including any prior diagnosis of liver disease, ischemic heart disease, cardiac failure, or acute coronary syndrome.

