Appendix 1. Codes used in data abstraction

Diagnostic codes used to Abstract the Danish National Registry of Patients and the Registry of Causes of Death

Disease/condition	ICD-8 code	ICD-10 code
Diabetes type 1	249.00; 249.06; 249.07; 249.09	E10.0, E10.1; E10.9
Diabetes type 2	250.00; 250.06; 250.07; 250.09	E11.0; E11.1; E11.9
Acute myocardial infarction	410	I21, I22, I23
Ischemic heart disease (acute and chronic)	411-414	I20, I24, I25
Congestive heart failure	427.09, 427.10, 427.11, 427.19, 428.99, 782.49;	I50, I11.0, I13.0, I13.2
Other cardiac disease	393–398, 400–404	I05–I09
Peripheral vascular disease	440, 441, 442, 443, 444, 445	I70, I71, I72, I73, I74, I77
Ischemic stroke	430-438 (cerebrovascular disease)	I63-64
Alcoholism	291, 303, 577.10, 571.09, 571.10	F10.1-F10.9, G31.2, G62.1, G72.1, I42.6, K29.2, K86.0, Z72.1
Obesity	277.99	E65-E66
Mild liver disease	571, 573.01, 573.04	B18, K70.0–K70.3, K70.9, K71, K73, K74, K76.0
Moderate to severe liver disease	070.00, 070.02, 070.04, 070.06, 070.08, 573.00, 456.00–456.09	B15.0, B16.0, B16.2, B19.0, K70.4, K72, K76.6, I85
Deep vein thrombosis	451.00	I81, I82
Pulmonary embolism	450.99	I26

ICD-8: http://www.sst.dk/Indberetning%20og%20statistik/Klassifikationer/SKS_download.aspx

ICD-10: <http://apps.who.int/classifications/apps/icd/icd10online/>

Diagnostic codes used to compute Charlson Comorbidity Index¹⁹

Disease	ICD-8 code	ICD-10 code
Myocardial infarction	410	I21;I22;I23
Congestive heart failure	427.09; 427.10; 427.11; 427.19; 428.99; 782.49	I50; I11.0; I13.0; I13.2
Peripheral vascular disease	440; 441; 442; 443; 444; 445	I70; I71; I72; I73; I74; I77
Cerebrovascular disease	430-438	I60-I69; G45; G46
Dementia	290.09-290.19; 293.09	F00-F03; F05.1; G30
Chronic pulmonary disease	490-493; 515-518	J40-J47; J60-J67; J68.4; J70.1; J70.3; J84.1; J92.0; J96.1; J98.2; J98.3
Connective tissue disease	712; 716; 734; 446; 135.99	M05; M06; M08; M09;M30;M31; M32; M33; M34; M35; M36; D86
Ulcer disease	530.91; 530.98; 531-534	K22.1; K25-K28
Mild liver disease	571; 573.01; 573.04	B18; K70.0-K70.3; K70.9; K71; K73; K74; K76.0
Diabetes type1	249.00; 249.06; 249.07; 249.09	E10.0, E10.1; E10.9
Diabetes type2	250.00; 250.06; 250.07; 250.09	E11.0; E11.1; E11.9
Hemiplegia	344	G81; G82
Moderate to severe renal disease	403; 404; 580-583; 584; 590.09; 593.19; 753.10- 753.19; 792	I12; I13; N00-N05; N07; N11; N14; N17-N19; Q61
Diabetes with end organ damage type1	249.01-249.05; 249.08	E10.2-E10.8

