 C109B11 TYPE II DIABETES MELLITUS WITH POLYNEUROPATHY
 C109C00 NON-INSULIN DEPENDENT DIABETES MELLITUS WITH NEPHROPATHY
 C109C11 TYPE II DIABETES MELLITUS WITH NEPHROPATHY
 C109D00 NON-INSULIN DEPENDENT DIABETES MELLITUS WITH HYPOGLYCA COMA
 C109D11 TYPE II DIABETES MELLITUS WITH HYPOGLYCAEMIC COMA
 C109E00 NON-INSULIN DEPEND DIABETES MELLITUS WITH DIABETIC CATARACT
 C109E11 TYPE II DIABETES MELLITUS WITH DIABETIC CATARACT
 C109F00 NON-INSULIN-DEPENDENT D M WITH PERIPHERAL ANGIOPATHY
 C109F11 TYPE II DIABETES MELLITUS WITH PERIPHERAL ANGIOPATHY
 C109G00 NON-INSULIN DEPENDENT DIABETES MELLITUS WITH ARTHROPATHY
 C109G11 TYPE II DIABETES MELLITUS WITH ARTHROPATHY
 C109H00 NON-INSULIN DEPENDENT D M WITH NEUROPATHIC ARTHROPATHY
 C109H11 TYPE II DIABETES MELLITUS WITH NEUROPATHIC ARTHROPATHY
 C10A.00 MALNUTRITION-RELATED DIABETES MELLITUS
 C10A000 MALNUTRITION-RELATED DIABETES MELLITUS WITH COMA
 C10A100 MALNUTRITION-RELATED DIABETES MELLITUS WITH KETOACIDOSIS
 C10B.00 DIABETES MELLITUS INDUCED BY STEROIDS
 C10B000 STEROID INDUCED DIABETES MELLITUS WITHOUT COMPLICATION
 C10y.00 DIABETES MELLITUS WITH OTHER SPECIFIED MANIFESTATION
 C10y100 DIABETES MELLITUS, ADULT, + OTHER SPECIFIED MANIFESTATION
 C10yy00 OTHER SPECIFIED DIABETES MELLITUS WITH OTHER SPEC COMPS
 C10yz00 DIABETES MELLITUS NOS WITH OTHER SPECIFIED MANIFESTATION
 C10z.00 DIABETES MELLITUS WITH UNSPECIFIED COMPLICATION
 C10z100 DIABETES MELLITUS, ADULT ONSET, + UNSPECIFIED COMPLICATION
 C10zz00 DIABETES MELLITUS NOS WITH UNSPECIFIED COMPLICATION
 C350011 BRONZED DIABETES
 Cyu2.00 [X]DIABETES MELLITUS
 Cyu2000 [X]OTHER SPECIFIED DIABETES MELLITUS
 F171100 AUTONOMIC NEUROPATHY DUE TO DIABETES
 F345000 DIABETIC MONONEURITIS MULTIPLEX
 F35z000 DIABETIC MONONEURITIS NOS
 F372.00 POLYNEUROPATHY IN DIABETES
 F372.11 DIABETIC POLYNEUROPATHY
 F372.12 DIABETIC NEUROPATHY
 F372000 ACUTE PAINFUL DIABETIC NEUROPATHY
 F372100 CHRONIC PAINFUL DIABETIC NEUROPATHY
 F372200 ASYMPTOMATIC DIABETIC NEUROPATHY
 F381300 MYASTHENIC SYNDROME DUE TO DIABETIC AMYOTROPHY
 F381311 DIABETIC AMYOTROPHY
 F3y0.00 DIABETIC MONONEUROPATHY
 F420.00 DIABETIC RETINOPATHY
 F420000 BACKGROUND DIABETIC RETINOPATHY
 F420100 PROLIFERATIVE DIABETIC RETINOPATHY
 F420200 PREPROLIFERATIVE DIABETIC RETINOPATHY
 F420300 ADVANCED DIABETIC MACULOPATHY

F420400 DIABETIC MACULOPATHY
 F420500 ADVANCED DIABETIC RETINAL DISEASE
 F420z00 DIABETIC RETINOPATHY NOS
 F440700 DIABETIC IRITIS
 F464000 DIABETIC CATARACT
 G73y000 DIABETIC PERIPHERAL ANGIOPATHY

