 G58z.12 Cardiac failure NOS
 G5y3.00 Cardiomegaly
 G5y3.11 Dilatation - cardiac
 G5y3000 Atrial dilatation
 G5y3100 Ventricular dilatation
 G5y3200 Cardiac dilatation NOS
 G5y3300 Atrial hypertrophy
 G5y3400 Ventricular hypertrophy
 G5y3411 Left ventricular hypertrophy
 G5y3500 Cardiac hypertrophy NOS
 G5y3z00 Cardiomegaly NOS
 8B29.00 Cardiac failure therapy
 R2y1000 [D]Cardiorespiratory failure
 324..00 ECG:left ventricle hypertrophy
 325..00 ECG:right ventricle hypertrop.
 G232.00 Hypertensive heart&renal dis wth (congestive) heart failure
 G234.00 Hyperten heart&renal dis+both(congestv) heart and renal fai
 G21z011 Cardiomegaly - hypertensive
 G31y000 Acute coronary insufficiency
 G34y000 Chronic coronary insufficiency
 G1yz100 Rheumatic left ventricular failure
 SP11111 Heart failure as a complication of care
 SP11200 Cardiorespiratory failure as a complication of care
 SP11100 Cardiac insufficiency as a complication of care
 P6yy200 Congenital cardiomegaly
 Q48y100 Congenital cardiac failure
 Q490.00 Neonatal cardiac failure
 14A6.00 H/O: heart failure
 14AM.00 H/O: Heart failure in last year

Congestive Heart Failure

G58..00 Heart failure
 G58..11 Cardiac failure
 G580.00 Congestive heart failure
 G580.11 Congestive cardiac failure

G580.12 Right heart failure
 G580.13 Right ventricular failure
 G580.14 Biventricular failure
 G580000 Acute congestive heart failure
 G580100 Chronic congestive heart failure
 G580200 Decompensated cardiac failure
 G580300 Compensated cardiac failure
 G581.00 Left ventricular failure
 G581.11 Asthma - cardiac
 G581.12 Pulmonary oedema - acute
 G581.13 Impaired left ventricular function
 G581000 Acute left ventricular failure
 G582.00 Acute heart failure
 G58z.00 Heart failure NOS
 G58z.11 Weak heart
 G58z.12 Cardiac failure NOS
 G5y3.00 Cardiomegaly
 G5y3.11 Dilatation - cardiac
 G5y3000 Atrial dilatation
 G5y3100 Ventricular dilatation
 G5y3200 Cardiac dilatation NOS
 G5y3300 Atrial hypertrophy
 G5y3400 Ventricular hypertrophy
 G5y3411 Left ventricular hypertrophy
 G5y3500 Cardiac hypertrophy NOS
 G5y3z00 Cardiomegaly NOS
 8B29.00 Cardiac failure therapy
 R2y1000 [D]Cardiorespiratory failure
 324..00 ECG:left ventricle hypertrophy
 325..00 ECG:right ventricle hypertrop.
 G232.00 Hypertensive heart&renal dis wth (congestive) heart failure
 G234.00 Hyperten heart&renal dis+both(congestv) heart and renal fai
 G21z011 Cardiomegaly - hypertensive
 G31y000 Acute coronary insufficiency

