G64z400	Infarction of basal ganglia
G65..00	Transient cerebral ischaemia
G65..11	Drop attack
G65..12	Transient ischaemic attack
G65..13	Vertebro-basilar insufficiency
G650.00	Basilar artery syndrome
G650.11	Insufficiency - basilar artery
G651.00	Vertebral artery syndrome
G651000	Vertebro-basilar artery syndrome
G652.00	Subclavian steal syndrome
G653.00	Carotid artery syndrome hemispheric
G654.00	Multiple and bilateral precerebral artery syndromes
G655.00	Transient global amnesia
G656.00	Vertebrobasilar insufficiency
G65y.00	Other transient cerebral ischaemia
G65z.00	Transient cerebral ischaemia NOS
G65z000	Impending cerebral ischaemia
G65z100	Intermittent cerebral ischaemia
G65zz00	Transient cerebral ischaemia NOS
G66..00	Stroke and cerebrovascular accident unspecified
G66..11	CVA unspecified
G66..12	Stroke unspecified
G66..13	CVA - Cerebrovascular accident unspecified
G660.00	Middle cerebral artery syndrome
G661.00	Anterior cerebral artery syndrome
G662.00	Posterior cerebral artery syndrome
G663.00	Brain stem stroke syndrome
G664.00	Cerebellar stroke syndrome
G665.00	Pure motor lacunar syndrome
G666.00	Pure sensory lacunar syndrome
G667.00	Left sided CVA
G668.00	Right sided CVA
G669.00	Cerebral palsy, not congenital or infantile, acute
G680.00	Sequelae of subarachnoid haemorrhage
G681.00	Sequelae of intracerebral haemorrhage
G682.00	Sequelae of other nontraumatic intracranial haemorrhage
G683.00	Sequelae of cerebral infarction
G68W.00	Sequelae/other + unspecified cerebrovascular diseases
G68X.00	Sequelae of stroke,not specfd as h'morrhage or infarction
G6W..00	Cereb infarct due unsp occlus/stenos precerebr arteries
G6X..00	Cerebrl infarctn due/unspcf occlusn or sten/cerebrl artrts

Chronic Liver Disease

A707.00	CHRONIC VIRAL HEPATITIS
A707000	CHRONIC VIRAL HEPATITIS B WITH DELTA-AGENT
A707100	CHRONIC VIRAL HEPATITIS B WITHOUT DELTA-AGENT
A707200	CHRONIC VIRAL HEPATITIS C

A707X00 CHRONIC VIRAL HEPATITIS, UNSPECIFIED
C310400 GLYCOGENOSIS WITH HEPATIC CIRRHOSIS
J61..00 CIRRHOSIS AND CHRONIC LIVER DISEASE
J610.00 ALCOHOLIC FATTY LIVER
J612.00 ALCOHOLIC CIRRHOSIS OF LIVER
J612.11 FLORID CIRRHOSIS
J612.12 LAENNEC'S CIRRHOSIS
J612000 ALCOHOLIC FIBROSIS AND SCLEROSIS OF LIVER
J613.00 ALCOHOLIC LIVER DAMAGE UNSPECIFIED
J613000 ALCOHOLIC HEPATIC FAILURE
J614.00 CHRONIC HEPATITIS
J614000 CHRONIC PERSISTENT HEPATITIS
J614100 CHRONIC ACTIVE HEPATITIS
J614111 AUTOIMMUNE CHRONIC ACTIVE HEPATITIS
J614200 CHRONIC AGGRESSIVE HEPATITIS
J614300 RECURRENT HEPATITIS

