J614400 CHRONIC LOBULAR HEPATITIS
J614y00 CHRONIC HEPATITIS UNSPECIFIED
J614z00 CHRONIC HEPATITIS NOS
J615.00 CIRRHOSIS - NON ALCOHOLIC
J615.11 PORTAL CIRRHOSIS
J615000 UNILOBULAR PORTAL CIRRHOSIS
J615100 MULTILOBULAR PORTAL CIRRHOSIS
J615111 POSTNECROTIC CIRRHOSIS OF LIVER
J615200 MIXED PORTAL CIRRHOSIS
J615300 DIFFUSE NODULAR CIRRHOSIS
J615400 FATTY PORTAL CIRRHOSIS
J615500 HYPERTROPHIC PORTAL CIRRHOSIS
J615600 CAPSULAR PORTAL CIRRHOSIS
J615700 CARDIAC PORTAL CIRRHOSIS
J615711 CONGESTIVE CIRRHOSIS
J615800 JUVENILE PORTAL CIRRHOSIS
J615811 CHILDHOOD FUNCTION CIRRHOSIS
J615812 INDIAN CHILDHOOD CIRRHOSIS
J615900 PIGMENTARY PORTAL CIRRHOSIS
J615A00 PIPE-STEM PORTAL CIRRHOSIS
J615B00 TOXIC PORTAL CIRRHOSIS
J615C00 XANTHOMATOUS PORTAL CIRRHOSIS
J615D00 BACTERIAL PORTAL CIRRHOSIS
J615E00 CARDITUBERCULOUS CIRRHOSIS
J615F00 SYPHILITIC PORTAL CIRRHOSIS
J615G00 ZOOPARASITIC PORTAL CIRRHOSIS
J615H00 INFECTIOUS CIRRHOSIS NOS
J615y00 PORTAL CIRRHOSIS UNSPECIFIED
J615z00 NON-ALCOHOLIC CIRRHOSIS NOS
J615z11 MACRONODULAR CIRRHOSIS OF LIVER
J615z12 CRYPTOGENIC CIRRHOSIS OF LIVER
J615z13 CIRRHOSIS OF LIVER NOS
J615z14 LAENNEC'S CIRRHOSIS, NON-ALCOHOLIC
J615z15 HEPATIC FIBROSIS
J616.00 BILIARY CIRRHOSIS

J616000 PRIMARY BILIARY CIRRHOSIS
 J616100 SECONDARY BILIARY CIRRHOSIS
 J616200 BILIARY CIRRHOSIS OF CHILDREN
 J616z00 BILIARY CIRRHOSIS NOS
 J617000 CHRONIC ALCOHOLIC HEPATITIS
 J61y.00 OTHER NON-ALCOHOLIC CHRONIC LIVER DISEASE
 J61y000 CHRONIC YELLOW LIVER ATROPHY
 J61y100 NON-ALCOHOLIC FATTY LIVER
 J61y700 STEATOSIS OF LIVER
 J61yz00 OTHER NON-ALCOHOLIC CHRONIC LIVER DISEASE NOS
 J61z.00 CHRONIC LIVER DISEASE NOS
 J62..00 LIVER ABSCESS AND SEQUELAE OF CHRONIC LIVER DISEASE
 J625.00 [X] HEPATIC FAILURE
 J625.11 [X] LIVER FAILURE
 J62y.00 OTHER SEQUELAE OF CHRONIC LIVER DISEASE
 J62y.11 HEPATIC FAILURE NOS
 J62y.12 LIVER FAILURE NOS
 J62y.13 HEPATIC FAILURE
 J62z.00 LIVER ABSCESS AND CHRONIC LIVER DISEASE CAUSING SEQUELAE NOS
 J635300 TOXIC LIVER DISEASE WITH CHRONIC PERSISTENT HEPATITIS
 J635400 TOXIC LIVER DISEASE WITH CHRONIC LOBULAR HEPATITIS
 J635500 TOXIC LIVER DISEASE WITH CHRONIC ACTIVE HEPATITIS
 J635600 TOXIC LIVER DISEASE WITH FIBROSIS AND CIRRHOSIS OF LIVER
 SP14200 HEPATIC FAILURE AS A COMPLICATION OF CARE
 SP14211 LIVER FAILURE AS A COMPLICATION OF CARE

Venous Thromboembolism (both deep venous thrombosis and pulmonary embolism)

G801.11 Deep vein thrombosis
 G801.12 Deep vein thrombosis, leg
 G801.13 DVT - Deep vein thrombosis

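### Several Appendix 1 code lists do not match the section 3.4 endpoints or each other across countries, so some per-country proportions and the UK stroke endpoint would be misclassified to an unknown degree

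*Protocol*

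**What the plan says.** Protocol section 3.4 makes Appendix 1 the complete source of definitions: "All codes relevant to abstracting diagnostic, drug, and laboratory data appear in Appendix 1". The lists are therefore fixed in this document.

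- **Liver.** Section 3.4.1 names "History of hepatic impairment (moderate to severe liver disease". Section 3.6.2 describes the before/after analysis as "including any prior diagnosis of liver disease, ischemic heart disease, cardiac failure, or acute coronary syndrome". Denmark has separate mild and moderate-to-severe rows. The UK has one chronic liver disease list, which includes "J61y100 NON-ALCOHOLIC FATTY LIVER".
- **Peripheral vascular disease (PVD).** Section 3.6.2 includes it in the minimum analysis around the 2008 press release. The UK PVD list gives diabetic peripheral angiopathy as RG73y000; the UK diabetes list gives "G73y000 DIABETIC PERIPHERAL ANGIOPATHY".
- **Heart failure.** Section 3.4.1 has one item for heart failure or ischaemic heart disease. The UK heart failure list includes "324..00 ECG:left ventricle hypertrophy". The Danish ICD-10 row is I50, I11.0, I13.0 and I13.2.
- **Type 1 diabetes.** It is an off-label criterion for both countries (section 3.4.2). The Danish ICD-10 entry is "E10.0, E10.1; E10.9". The only UK diabetes list is headed as non-specific and Type II.
- **Stroke.** Section 3.4.3 wants new cerebrovascular accident or ischaemic stroke. The only UK list is a combined TIA and stroke list, with entries such as "Sequelae of subarachnoid haemorrhage". Denmark uses I63-64 in ICD-10.

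**The concern.** Contraindicated use and off-label use are specific aims of the study, and section 3.6.2 promises proportions for each country and over time. Each proportion is only as good as the code list behind it. A list that is too broad counts people without the condition, one that is too narrow misses people with it, and one in the wrong format finds nobody. If the lists also differ between Denmark and the UK, a difference between the two proportions cannot be separated from a difference in definition. For the 45-day stroke outcome, codes that do not denote a new stroke would enter the UK numerator and have no Danish counterpart.

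**Working it through.** The plan states no figure that could be reproduced here. The check sets each endpoint beside its list and counts codes in Appendix 1.

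**1. PVD, UK.** The list holds 23 codes, and all begin RG73. G73y000 has 7 characters; RG73y000 has 8. UK diagnostic codes that legitimately begin with R, such as R054200 and R2y1000, also have 7, so R is not a general eighth character. The same term thus appears in two forms, and the 8-character form is the odd one out. Run literally, 0 of the 23 would match. Even without the prefix, the UK list covers the G73 group only, while the Danish row spans I70-I74 and I77.

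**2. Type 1 diabetes.**

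| | Abstraction row | Charlson table, type 1 with end-organ damage |
|---|---|---|
| ICD-10 | E10.0, E10.1, E10.9 | E10.2-E10.8 |
| ICD-8 | 249.00, 249.06, 249.07, 249.09 | 249.01-249.05, 249.08 |

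The appendix itself labels the right-hand codes type 1, yet the abstraction row leaves them out. The UK has no type 1 codes. The same search finds no UK codes for gestational diabetes or polycystic ovary syndrome, which section 3.4.2 names as UK-only criteria.

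**3. Stroke, UK.** Codes by block: G63 13, G64 18, G65 18, G66 14, G68 6, G6W and G6X 2.

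- Total: 13 + 18 + 18 + 14 + 6 + 2 = 71.
- G65 is the transient-ischaemia block, which also holds drop attack and transient global amnesia: 18.
- G68 is sequelae, including those of haemorrhage: 6.
- Together: (18 + 6)/71 = 24/71 = 34% of codes.
- Carotid stenosis, within G63, comes on top of this.

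The Danish ICD-8 range (430-438, all cerebrovascular disease) is also wider than I63-64. Section 6.1 puts ICD-10 in use since 1994, so the ICD-8 range bears only on screening out prior events.

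**4. Heart failure, UK.** The list holds 48 codes.

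- Cardiomegaly, dilatation and hypertrophy: the G5y3 block (10), G21z011 and P6yy200, which makes 12.
- ECG hypertrophy: 324..00 and 325..00, which makes 2.
- Subtotal: 12 + 2 = 14 of 48 (29%).
- Coronary insufficiency: G31y000 and G34y000 bring this to 16 of 48 (33%).

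The Danish ICD-10 row has no counterpart to these.

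**5. Liver.** The UK list holds 80 codes, of which 8 name hepatic or liver failure. The wording of the other 72 does not limit them to moderate or severe disease. Under section 3.4.1 the UK list is too broad. Under section 3.6.2 the UK list fits, and the Danish moderate-to-severe row is too narrow on its own. The countries are unmatched on either reading unless the Danish or the UK scope is changed.

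**The case against.** Much can be said for the plan.

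- **PVD.** A reader might infer that UK PVD capture will be zero. That holds only if the list is run literally. The R is uniform and the terms are intact. The UK nitrate list also prints a prefix (B06106) where the antiplatelet list prints plain numbers (6105), so an export artefact is plausible. A zero count among about 20,000 users would be noticed. Extremity-artery atheroma also appears under the UK cardiovascular list. This stands: it is a transcription fault, though one to correct before extraction.
- **Stroke.** The UK list is not labelled as an outcome list. Section 3.4.3 identifies both acute and pre-existing events and screens out the latter, and stenosis and sequelae codes suit that purpose. This stands in part: the plan assigns the list no role, so nothing keeps those codes out of the outcome. A reader might go further and infer a specific dilution of the risk ratio. That would need the non-stroke share of events and the risk ratio for those events, and the documents give neither.
- **Heart failure.** Section 3.4.1 combines heart failure with ischaemic heart disease, so the coronary-insufficiency codes do not misclassify that item. This stands. The other 14 codes remain a problem.
- **Country comparison.** The spline comparison in section 3.6.1 is conditional and concerns prescribing. Within one country the same list applies before and after 2008, so an over-broad list mainly shifts the level. This stands, but section 3.6.2 still commits to proportions in each country.
- **Type 1.** Up to 20 diagnoses per contact and records from 1977 mean that some Danish patients with complications will also carry an included code. Undercounting is therefore partial.

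**Conclusion.** The point holds as a set of mismatches visible in the protocol itself. Run as written, the lists would misclassify some contraindicated and off-label proportions and the UK 45-day stroke endpoint, and differences between countries would be partly artefactual. The PVD fault matters most: it affects the minimum before/after-2008 analysis in the database that holds about 20,000 of about 22,400 users (20,000 + 2,400).

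The size is unknown. The counts (23 of 23, 24 of 71, 14 of 48) are shares of codes, not of patients or events, and no prevalences are given. Three stronger readings are not supported: that every list is affected (the myocardial infarction lists broadly correspond), that country differences are wholly artefactual, and that the UK liver list is plainly the wrong one. The liver question cannot be settled until sections 3.4.1 and 3.6.2 agree.

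**What to change.** Before extraction:

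1. **PVD:** remove the leading R from the 23 UK codes and confirm non-zero counts.
2. **Type 1 diabetes:** add E10.2-E10.8 and ICD-8 249.01-249.05 and 249.08 to the Danish row, and add a UK type 1 list.
3. **Stroke:** state the role of the UK list. Use only acute infarction and stroke codes for the 45-day outcome; keep transient ischaemia, stenosis and sequelae for screening out prior events.
4. **Heart failure:** remove the 14 hypertrophy, cardiomegaly, dilatation and ECG-hypertrophy codes, and move the two coronary-insufficiency codes to ischaemic heart disease. The same block is repeated under the UK cardiovascular list and needs the same edit if that list serves this endpoint.
5. **Liver:** reconcile sections 3.4.1 and 3.6.2, then apply one severity scope to both countries. If moderate to severe is kept, state which UK codes qualify.

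The cost is list editing and count checks; no new data are needed. There will be fewer UK heart failure and stroke cases, and fewer UK liver cases if the narrower scope is kept. With only 8 of 80 UK liver terms naming failure, that last reduction could be large.
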